
Objectives:
 
Primary
 
 • To evaluate the efficacy of Cannabidiol Oral Solution as adjunctive therapy with vigabatrin as initial therapy in treating patients with Infantile Spasms. 
Secondary
 
 • To evaluate the continued efficacy of Cannabidiol Oral Solution after the 14-day treatment with vigabatrin or vigabatrin plus Cannabidiol Oral Solution is complete. • To evaluate the safety and tolerability of Cannabidiol Oral Solution as adjunctive therapy with vigabatrin as initial therapy in treating patients with Infantile Spasms.

Methodology:
 
This is a Phase 3, double-blind, placebo-controlled, randomized, multicenter study to evaluate the efficacy, safety, and tolerability of Cannabidiol Oral Solution (CBD) as adjunctive therapy with vigabatrin as initial therapy, compared to vigabatrin alone in the treatment of infants newly diagnosed with Infantile Spasms (IS). Randomization will occur during Visit 2 to one of two treatment groups:
 
 • Treatment with vigabatrin plus 
 o CBD 40 mg/kg/day, or o Matching CBD 40 mg/kg/day placebo

Approximately 190 patients in total will be enrolled into one of the two treatment arms; 130 patients in the investigational product arm with 60 patients in the placebo arm. Patients will be dosed approximately every 12 hours with meals to help ensure consistent plasma levels are achieved and to reduce variability.

Doses of CBD exceeding 40 mg/kg/day will not be examined in this study. In addition to the safety assessments required by the study protocol, the investigator will monitor patients throughout the study as recommended in the current approved product label for vigabatrin. Study participants will be newly diagnosed pediatric patients age 1 to 24 months (inclusive) experiencing infantile spasms who satisfy all inclusion/exclusion criteria. This study will be comprised of five periods: Screening, Initial Treatment, Extended Treatment, Taper, and Follow-up Periods, with a maximum duration of approximately 140 days.

Screening Period:

Each newly diagnosed patient with Infantile Spasms will complete a Screening Period and will have up to 14 days to enroll in the study.

Patients will have a minimum of a 9-hour video-EEG that includes at least one full sleep-wake cycle during their Screening Visit to establish their baseline level of infantile spasms and hypsarrythmia and a 24-hour video-EEG at Visit 5 (Day 14) of the Initial Treatment Period to establish their final level of infantile spasms and hypsarrythmia. A blinded central reader, not involved in the study, will evaluate the video-EEGs and determine responder status. Details of the video-EEG assessment will be provided in the video-EEG Charter. The treatment response categories are summarized in Table 1 below. In addition, a 9-hour video EEG will be conducted during the Extended Treatment Period to confirm parent/caregiver reports of relapse. If possible, a 9-hour video EEG will be conducted for patients who have continued into the Extended Treatment Period and decided to Early Withdraw. A video EEG is not required for patients who decide to withdraw during the Initial Treatment Period.

Table 1: Video EEG Response Definitions

Response Category	Definition
Complete Response	Complete resolution of spasms and hypsarrythmia confirmed by video EEG
Partial Response	Complete resolution of either spasms or hypsarrythmia confirmed by video EEG
Non-Response	No improvement or worsening of spasms/hypsarrythmia burden

Initial Treatment Period

- Day 1 (Visit 2): Patients will receive the initial titration dose of vigabatrin (50 mg/kg/day divided twice daily [BID]), and either CBD 20 mg/kg/day plus matching CBD 20 mg/kg/day placebo or CBD 40 mg/kg/day placebo, each drug administered BID for 3 days.
- Day 4 (Visit 3): Patients will return to the study center to evaluate medical status (seizure diary, vital signs, and neurological exam), clinical laboratory assessments,

concomitant medications, height/weight, and assess adverse events (AEs). For those patients who tolerate the initial dose, the dose for vigabatrin will be increased to 100 mg/kg/day (BID), and either CBD 30 mg/kg/day and matching CBD 10 mg/kg/day placebo, or CBD 40 mg/kg/day placebo BID for 3 days.

- Day 7 (Visit 4): Patients will return to the study center to evaluate medical status (seizure diary, vital signs, and neurological exam), clinical laboratory assessments, concomitant medications, height/weight, and assess AEs. For those patients who tolerate the increased doses, the dose of vigabatrin will be increased to 150 mg/kg/day and CBD or CBD placebo to 40 mg/kg/day BID for the remaining 9 days. Vigabatrin, CBD, and matching placebo will be administered in a twice daily fashion at 12-hour intervals with meals.
- As part of their standard of care, investigators will assess safety and tolerability of the treatment regimens throughout the study period. All subjects will continue treatment until confirmation from the central reader on the 24-hour video EEG and clinical laboratory results are received.

Extended Treatment Period

Following the Initial Treatment Period:

- Complete Responders will continue receiving their assigned treatments of vigabatrin plus either CBD 40 mg/kg/day or matching placebo for 75 days, until Week 13 (Day 90) to monitor treatment response.
- During the Extended Treatment Period, the investigator may reduce the dose of CBD or CBD placebo to 30 mg/kg/day for safety or tolerability. If the subjects cannot tolerate the 30 mg/kg/day, they will be discontinued from the study following the completion of the taper period.

Partial Responders:

Partial responders will be offered the opportunity to enroll in an open-label safety study that allows investigators to combine standard-of-care treatment with CBD.

Taper Period

Following the completion of the Initial Treatment Period (Visit 6), partial responders who do not enroll in the open-label safety study and non-responders will have vigabatrin and CBD or CBD placebo tapered as follows:

- Vigabatrin taper: 150 mg/kg/day will be reduced to 100 mg/kg/day for 3 days, then the 100 mg/kg/day dose will be reduced to 50 mg/kg/day for 3 days, and then discontinued.
- CBD or CBD Placebo taper: 40 mg/kg/day will be reduced to 30 mg/kg/day for three days, then 30 mg/kg/day will be reduced to 20 mg/kg/day for 3 days, and then discontinued.

Complete Responders will be tapered off vigabatrin and CBD at the completion of the Extended Treatment Period, and all patients will be tapered off at any Early Withdrawal Visits, using the same schedules as described above.

If the investigator decides to continue vigabatrin as a treatment for patients at the end of the study or early withdrawal, tapering of vigabatrin will be left to the discretion of the PI.

CBD requires tapering off at the End of Study or at the Early Withdrawal visit.

Follow-up Period

A follow-up phone call will occur for all subjects 30 days after discontinuation of the study drug to assess AEs, AETs, and record concomitant medications.

Study Assessments

To assess efficacy, a 24-hour video-EEG, daily seizure diaries, meal diary 24 hours prior to and through PK blood sampling and investigator Clinical Global Impressions-Global Improvement (CGI-I) assessments will be completed and evaluated.

- A 9-hour video EEG that includes at least one sleep-wake cycle will be completed during Screening (Visit 1) and a 24-hour video EEG will be completed Day 14 (Visit 5) through Day 15 (Visit 6). The EEGs and hypsarrhythmia will be evaluated by a blinded central reader who is not involved with the study. Further details will be provided in the video-EEG Charter.
- Daily seizure diaries will be completed throughout the Initial and Extended Treatment Periods.
- The CGI-I will be completed by the investigator at Visit 6 of the Initial Treatment Period, or at Early Withdrawal. The CGI-S will be completed by the investigator at Screening.

Safety assessments for all patients will include medical history, physical and neurological examinations, vital signs (seated or supine blood pressure [depending on patient age and ability], pulse rate, temperature, and respiration rate), clinical laboratory testing (hematology, chemistry, liver enzymes, and serum bilirubin), prior medication history (assessment of past/current AETs and concomitant medications), and AE assessments will be conducted at specific visits throughout the study. In addition to the safety assessments required by the study protocol, the investigator will monitor patients as recommended in the current FDA-approved vigabatrin prescribing information.

A blood sample for PK analysis of CBD and the metabolite 7-hydroxy-CBD (7-OH-CBD) will be obtained on Day 15 prior to the second dose during the 24-hour video-EEG. A meal diary will be used to record the type of meals consumed in relation to PK blood draws.

If a patient discontinues the study prematurely, the investigator's impression of efficacy and tolerability of the study drug, as evaluated by CGI-I, will be assessed and recorded immediately before discontinuation. If possible, the parent/caregiver will be encouraged to have the patient have an Early Withdrawal video-EEG completed.

Number of patients planned:

Approximately 190 patients (130 patients in the active drug arm and 60 patients in the placebo arm).

Diagnosis and main criteria for inclusion:

Patients will be male and female patients between 1 and 24 months of age (inclusive), with a new clinical diagnosis of Infantile Spasms, confirmed by video-EEG analysis during the Screening Period, have adequate renal and hepatic function, and who meet all the inclusion and none of the exclusion criteria. Parent(s)/caregiver(s) must be able to understand and provide written consent.

Inclusion criteria

A patient will be eligible for study participation if the patient meets all of the following criteria:

1. Parent(s)/caregiver(s) fully comprehends and signs the informed consent form, understands all study procedures, and can communicate satisfactorily with the Investigator and study coordinator, in accordance with applicable laws, regulations, and local requirements.
2. Male or female between 1 month to 24 months of age (inclusive) at time of consent.
3. Clinical diagnosis of Infantile Spasms, confirmed by video-EEG (including at least one cluster of electroclinical spasms [≥ 3 in any 10-minute epoch] and hypsarrhythmia) obtained during the Screening Period and read by a central reader.
4. General good health (defined as the absence of any clinically relevant abnormalities as determined by the Investigator) based on physical and neurological examinations, medical history, and clinical laboratory values completed during the Screening Visit (Visit 1).
5. In the opinion of the investigator, the parent(s)/caregiver(s) is (are) willing and able to comply with the study procedures and visit schedules.

Exclusion criteria

A patient must not meet any of the following criteria:

1. Is considered by the investigator, for any reason (including, but not limited to, the risks described as precautions, warnings, and contraindications in the current version of the [Investigator's Brochure](#) for Cannabidiol Oral Solution) to be an unsuitable candidate to receive the study drug.
2. Known or suspected allergy to cannabidiol.
3. History of an allergic reaction or a known or suspected sensitivity to any substance that is contained in the investigational product formulation.
4. Use of any cannabidiol/cannabis product within 30 days of study entry.
5. Patient is diagnosed or suspected of having tuberous sclerosis.

6. Patient has received treatment with either vigabatrin, ACTH, or high-dose steroids previously.
7. Previous or concomitant therapy with felbamate, clobazam, valproic acid, or the ketogenic diet.
8. Patient currently on any disallowed CYP3A4-related medication listed in [Appendix 1](#) (phenytoin, fluvoxamine, carbamazepine, and St. John's Wort).
9. Previously received any investigational drug or device or investigational therapy within 30 days before Screening.
10. Clinically significant abnormal laboratory values, including: liver function tests (LFTs) such as albumin, direct bilirubin, total bilirubin, aspartate aminotransferase (AST), and alanine aminotransferase (ALT) ≥ 3 times the upper limit of normal (ULN). The investigator may deem the patient eligible if he or she judges the laboratory values to be not clinically significant.

Investigational product, dosage, and mode of administration:

Cannabidiol Oral Solution, manufactured for and supplied by Insys Manufacturing LLC. During the Initial Treatment Period: 20, 30, and 40 mg/kg CBD BID. During the Extended Treatment Period: 40 mg/kg CBD BID (or 30 mg/kg if dose is reduced) for Complete Responders.

Duration of treatment:

The maximum duration of the study from screening to follow-up of AEs will be approximately 140 days.

Reference therapy, dosage, and mode of administration:

Vigabatrin powder suspension divided twice daily with food, 50 mg/kg/day for 3 days, then 100 mg/kg/day for 3 days, then 150 mg/kg/day for 9 days.

Criteria for evaluation:**Efficacy**Primary efficacy endpoint

- Percent of patients who are considered complete responders, defined as complete resolution of spasms and hypsarrhythmia confirmed by 24-hour video EEG from Day 14 to Day 15, as determined by the Independent Central Reader.

Secondary efficacy endpoints

- Percent of patients with resolution of infantile spasms as assessed by 24-hour video EEG from Day 14 to Day 15 (partial response).
- Percent of patients with resolution of hypsarrhythmia as assessed by 24-hour video EEG from Day 14 to Day 15 (partial response).
- Investigator impression of efficacy and tolerability of study drug (CGI-I) at Visit 6 (End of Study) or Early Withdrawal.
- Increase in the number of spasm-free days between Day 1 and Day 15 of the Initial Treatment Period, as determined by the seizure diary entries.
- For patients with a complete response during the Initial Treatment Period who continue: percent of patients who relapse during the Extended Treatment Period confirmed by video EEG following parent report of relapse, and time to relapse.

Safety

The safety endpoints of the study are the incidence of treatment-emergent AEs (TEAEs), clinical laboratory assessments, vital signs (blood pressure, pulse rate, respiration rate, and temperature), physical and neurological examination assessments, prior and concomitant medications, liver enzymes and serum bilirubin.

Pharmacokinetics

Trough concentrations (C_{trough}) of cannabidiol (CBD) and 7-OH-CBD will be used to assess the exposure-response relationship. A meal diary will be used to record the type of meals consumed in relation to the PK blood draws.

Statistical methods:**Sample Size Calculation**

A total of 190 patients (130 and 60 patients in the two groups) will provide 80% power with a two-sided alpha of 0.05 to detect a difference in response rate, assuming the response with vigabatrin alone is 40% and the response with vigabatrin with Cannabidiol Oral Solution is 60%.

Analysis Populations

Statistical analyses will be conducted on the following populations:

- Safety Population: The Safety Population will include all patients who were treated with at least one dose of the study drug.
- Intent to Treat (ITT) Population: The ITT Population will include all patients who were randomized.
- PK Population: The PK Population will include all patients who were treated with at least one dose of the study drug and have at least one usable PK measurement.

Efficacy Analyses

The ITT Population will be used for all efficacy analyses in the Initial Treatment Period.

- For the primary endpoint, a 2-sided Type I error rate of 0.05 will be used.
- For the secondary efficacy endpoints, to maintain the trial-wise Type I error rate at 0.05, a fixed sequence multiple comparisons correction with fallback will be used. The assignment of alpha levels to hypotheses being tested will be specified in the Statistical Analysis Plan.
- For endpoints that are continuous in nature, the number of observations, mean, median, minimum and maximum, and standard deviation (SD) values will be presented as descriptive statistics. For inferential statistics, a t-test will be used to compare treatment to placebo group.
- For endpoints that are categorical in nature, frequency, counts, and percentages will be presented as descriptive statistics, and a chi-square test will be used for inferential statistics.

Primary Efficacy Analysis

- Percent of patients with complete resolution of both infantile spasms and hypsarrhythmia at Day 15 (complete response) will be compared between vigabatrin plus placebo and vigabatrin plus CBD 40 mg/kg/day groups using a chi-square test.

Secondary Efficacy Analyses

- Percent of patients who relapse during the Extended Treatment Period will be compared between 14-day complete responders receiving vigabatrin + CBD and complete responders receiving 14-day vigabatrin + placebo using chi-square test. Time to relapse will be described with Kaplan-Meier curves and treatment groups compared using a log-rank test.

- Percent of patients with complete resolution of infantile spasms at Day 15 will be compared between treatment groups using a chi-square test.
- Percent of patients with complete resolution of hypsarrhythmia at Day 15 will be compared between treatment groups using a chi-square test.
- Investigator impression of efficacy and tolerability of study drug (Clinical Global Impression – Global Improvement [CGI-I]) will be compared between treatment groups using ANCOVA with baseline CGI-S as a covariate.
- Reduction in percentage of spasm-free days between the Initial Treatment Period and Screening Period will be compared between treatment groups using ANCOVA with the Screening Period percent spasm-free days as a covariate.

Secondary Efficacy Analyses for patients with a complete response during the Initial Treatment Period who continue to the Extended Treatment Period:

- Percent of patients who relapse during the Extended Treatment Period confirmed by video-EEG following parent report of relapse.
- Time to relapse.

Safety Analyses

The Safety Population will be used for all safety assessments. All safety assessments will be descriptive and no inferential statistics are planned for safety assessments. All data listings will be provided for protocol specified safety data.

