^e Vital signs will be taken after approximately 5 minutes seated or supine, depending on patient ability. On Day 1 (Visit 2), vital signs should be taken predose and at 4 hours postdose. On all other days, the assessment will be completed predose.

^f A brief neurological examination will be performed, except for the Screening Visit, Visit 6, Visit 9 and Early Withdrawal which will be a complete neurological exam. On Day 4 (Visit 3), and Day 7 (Visit 4) a brief neurological examination will be performed predose and approximately 2 hours following administration of the morning dose of the investigational product. Additional examinations may be performed at the discretion of the investigator.

^g On Day 1 (Visit 2), patients will receive the initial titration dose of vigabatrin (50 mg/kg/day divided twice daily [BID]), and either CBD 20 mg/kg/day plus matching CBD 20 mg/kg/day placebo or CBD 40 mg/kg/day placebo, each drug administered twice daily for three days.

^h For those patients who tolerate the initial dose, the dose for vigabatrin will be increased to 100 mg/kg/day [BID], and either CBD 30 mg/kg/day plus matching CBD 10 mg/kg/day, or CBD 40 mg/kg/day placebo for 3 days. On Day 7 (Visit 4) the dose of vigabatrin will be increased to 150 mg/kg/day and CBD to 40 mg/kg/day for the remaining 9 days for subjects who tolerate the previous dose.

ⁱ Complete Responders will continue receiving their assigned treatments of vigabatrin plus either CBD 40 mg/kg/day or matching placebo for 75 days, until Week 13 (Day 90) to monitor treatment response. During the extended treatment period the Investigator can only down titrate once to 30 mg/kg/day.

^j All subjects will be tapered off vigabatrin as follows: 150 mg/kg/day will be reduced to 100 mg/kg/day for 3 days then the 100 mg/kg/day will be reduced to 50 mg/kg/day for 3 days and then discontinued. Similarly, all subjects will be tapered off CBD or CBD Placebo according to the following schedule: 40 mg/kg/day will be reduced to 30 mg/kg/day for 3 days, then 30 mg/kg/day will be reduced to 20 mg/kg/day for 3 days, then discontinued. Patients will receive a follow-up phone call 4 weeks after completing the tapering. Drug reconciliation will be completed at the end of study.

^k A blood sample for PK analysis will be obtained on Day 15 prior to the second dose during the 24-hour video EEG.

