4.7.2. Prohibited Therapies

During the Screening, Initial Treatment, Extended Treatment, Taper, and Follow-up Periods, patients are not to receive the following:

- Any cannabinoids besides the investigational drug (other formulations of CBD, Δ^9 -THC, hemp oil, Realm Oil or marijuana). Exclusion criterion number 4 prohibits use within 30 days of study entry.
- Felbamate.
- Valproic acid.
- Clobazam.
- Corticotrophins.
- Medication(s) that are strong CYP3A4 inhibitors or inducers or CYP3A4-sensitive substrates with a narrow therapeutic index. A list of these medications is provided in [Appendix 1](#).
- Systemic steroid therapy (excluding inhaled medication for asthma treatment).
- Any other investigational drug or investigational device.
- Introduction of new anti-epileptic therapies (AETs) during the study is prohibited.

Patients must refrain from consumption of grapefruit, grapefruit juice, Seville oranges, Seville orange marmalade, or other products containing grapefruit or Seville oranges within 3 days of the first administration of investigational product and throughout the entire Treatment and Taper Periods.

Although they are not prohibited, patients taking concomitant medications may need to be monitored with special care to identify any AEs arising due to the potential for altered drug metabolism. This is discussed in detail in [Section 6.2.6.9](#).

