8.4.4.1. Adverse Events

The Medical Dictionary for Regulatory Activities (MedDRA, version 20.0) will be used to classify all AEs. Adverse event summaries will include only treatment-emergent AEs (TEAEs) by treatment group. Treatment-emergent adverse events (TEAEs) are defined as AEs that first occurred or worsened during the indicated treatment phase.

The number and percentage of patients with TEAEs will be summarized by system organ class (SOC) and preferred term (PT). Summaries of AEs by severity and relationship to the study treatment will also be provided. Serious adverse events (SAEs) and AEs resulting in discontinuation will be summarized separately in a similar manner. Patient listings of AEs and SAEs will be produced.

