### **11.2. Adverse Event Preferred Term and Body/Organ System Summary Tables**

Treatment Emergent Adverse Events (TEAEs) are defined as AEs that first occurred or worsened after the first administration of the investigational product. Adverse events are considered treatment-related if the relationship to study drug is related. A missing relationship will be imputed as related to study drug and included in the summary.

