#### **11.2.1. Summaries of Adverse Event Incidence Rates for All Subjects**

Overall summary of TEAE's will be summarized by any TEAE, treatment-related TEAE, treatment-related and severe TEAE, TEAE leading to study drug discontinuation, any serious TEAE, any serious and treatment related TEAE and TEAE resulting in death. Summaries of AEs will include incidence of TEAEs and treatment-related TEAEs by MedDRA preferred term (PT) and system organ class (SOC). The TEAEs will also be summarized by severity, PT, and SOC. Subjects reporting more than one TEAE are counted once in each category at the maximum severity.

AEs with a start date during the study will be summarized. Listings of all AEs, AEs leading to discontinuation of the study, SAEs, and deaths, if any, will be provided.

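### Protocol and SAP disagree on when the TEAE window ends, and neither closes it when a partial responder starts open-label CBD

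*Protocol*

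**What the plan says.** **Collection.** The protocol (Synopsis, Follow-up Period; Sections 3.1.5 and 7.2.6) states: "A follow-up phone call will occur for all subjects 30 days after discontinuation of the study drug to assess AEs, AETs". The Schedule of Events also marks AE assessment in the Taper and Follow-up columns. Infants who have moved to another study are not excepted.

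**Roll-over.** The Synopsis and Sections 3.1.3 and 4.1.3 state: "Partial responders will be offered the opportunity to enroll in an open-label safety study that allows investigators to combine standard-of-care treatment with CBD". The offer is not limited to one arm and carries no start date. The taper text (Section 3.1.4) requires tapering after Visit 6 only of non-responders and of partial responders who decline the open-label study.

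**Tabulation, protocol.** Section 8.4.4.1: "Adverse event summaries will include only treatment-emergent AEs (TEAEs) by treatment group". It adds that TEAEs "are defined as AEs that first occurred or worsened during the indicated treatment phase". Section 8.3 analyses the Safety Population by treatment actually received.

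**Tabulation, SAP.** Section 11.2: "Treatment Emergent Adverse Events (TEAEs) are defined as AEs that first occurred or worsened after the first administration of the investigational product". Section 11.2.1: "AEs with a start date during the study will be summarized". Both documents count Follow-up among the five periods of the study. The SAP's Safety Population (Section 6.4.1) does not carry the actual-treatment rule.

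**The concern.** Safety and tolerability is a secondary objective, and the evidence for it is a set of descriptive tables by arm. Those tables are interpretable only if the placebo column holds experience without CBD. A placebo infant who is a partial responder can start open-label CBD shortly after Visit 6 and then be asked, within this trial, about AEs over the 30 days after blinded drug stopped. The SAP's TEAE window is still open at that point. Events on the test drug, and on any standard-of-care drug added with it, can then enter the placebo column. The likely effect is to make the excess of AEs on CBD look smaller than it is.

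**Working it through.** There is no stated figure to reproduce. The check has two parts.

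**1. The two definitions applied to one infant.** Take a placebo partial responder who starts open-label CBD after Visit 6 and has a new AE ten days later.
- *Protocol 8.4.4.1:* the AE is outside the randomised treatment phase on a natural reading, so it is not a TEAE. However, the protocol does not define the phases or their end dates.
- *SAP 11.2 and 11.2.1:* the AE began after the first administration and, since Follow-up is a study period, during the study. It is a TEAE and goes in the infant's treatment-group column.
- *Protocol 8.3:* the actual-treatment rule assigns infants to columns, not events. The infant either stays under placebo with a CBD-period event, or moves to CBD with about 15 days of placebo experience. Neither result is clean.

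The answers conflict, and Section 8 of the protocol leaves detailed methods to the SAP.

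**2. Possible size.** Inputs from the protocol: 60 placebo infants, and assumed complete-response rates of 40% and 60%. The partial-response and roll-over rates are not given.

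Bound: 60 × (1 − 0.40) = 36 placebo infants are not complete responders, so between 0 and 36 could roll over.

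Illustration (all values assumed): true AE risk 30% on CBD and 10% on placebo; a share r of the arm rolls over, with r = 10%, 20% or 30% (6, 12 or 18 placebo infants); 30% risk in the first 30 open-label days among infants without an earlier event.

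- Placebo column = 0.10 + r × 0.90 × 0.30
- CBD column, equal roll-over and full renewed risk = 0.30 + r × 0.70 × 0.30
- CBD column, roll-over scaled by the ratio of non-complete responders = 0.30 + r × (0.40/0.60) × 0.70 × 0.30
- CBD column, no new events counted = 0.30

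| r | Placebo column | CBD column, equal roll-over | Excess, equal | Excess, scaled | Excess, CBD-arm events ignored |
|---|---|---|---|---|---|
| 10% | 12.7% | 32.1% | 19.4 | 18.7 | 17.3 |
| 20% | 15.4% | 34.2% | 18.8 | 17.4 | 14.6 |
| 30% | 18.1% | 36.3% | 18.2 | 16.1 | 11.9 |

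Excess is in percentage points; the true value is 20. With equal roll-over, the risk ratio falls from 3.0 to 2.5, 2.2 and 2.0.

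Direction: each unit of r adds 0.90 × 0.30 = 0.27 to the placebo column and at most 0.70 × 0.30 = 0.21 to the CBD column. The excess therefore shrinks unless CBD-arm infants roll over more than 0.27/0.21 = 1.29 times as often, at full renewed risk.

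**The case against.** The strongest reply is that no text says these events are counted against placebo. The follow-up sentence governs collection, and the protocol's own TEAE definition would leave them out. The SAP was also written for protocol V2.0 of 30 October 2017, under which placebo partial responders stayed on vigabatrin in the Extended Treatment Period, and it says that it may evolve with amendments. The problem therefore needs the current protocol's roll-over combined with the SAP's definition.

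This stands in part. A reader might infer that open-label events are certain to appear in the placebo column, and the documents do not support that. They support only that the SAP, followed as written, would put them there. That the SAP predates the roll-over explains the gap but does not close it.

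It is also fair that no open-label start date is given, so CBD use before the call is an inference. The exemption from taper, together with continued dosing until the central EEG reading arrives, makes a direct transition plausible but does not establish it. Whether the call reaches roll-over infants is itself unclear, because footnote j of the Schedule of Events times it at four weeks after a taper that Section 3.1.4 does not require of them.

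A reader might also infer that every roll-over is a prohibited-therapy deviation. Section 4.7.2 does say "During the Screening, Initial Treatment, Extended Treatment, Taper, and Follow-up Periods, patients are not to receive the following" and lists new antiepileptic therapies, but no text says how roll-over infants are to be classed, and open-label CBD may be the same investigational drug.

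Finally, safety is descriptive, and AEs and medications will be listed, so late events could be separated afterwards. That limits the harm. A prespecified cut-off is still better than separating events after unblinding.

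**Conclusion.** The two TEAE definitions conflict on where the window ends, and neither document sets a cut-off at open-label entry. Under the SAP wording the placebo column would take in AEs on open-label CBD, and the descriptive difference between arms would probably shrink. A bias of known size has not been shown. In the illustration the 20-point excess becomes 18.2–19.4 points with equal roll-over and full renewed risk, and 11.9–17.3 if CBD-arm events after roll-over are ignored. Quoting only the second range would overstate the effect, since the same call and window apply to CBD-arm infants. All of these figures rest on assumed roll-over and event rates. No sample size, power or primary-endpoint result is affected. The point should be settled when the SAP is updated to the current protocol, before unblinding.

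**What to change.** Put one TEAE definition in SAP Section 11.2 and protocol Section 8.4.4.1. The window opens at the first dose of investigational product and ends at the earlier of 30 days after the last blinded dose and the day before the first open-label dose. Make the summary rule in SAP 11.2.1 refer to that window, and list later AEs separately.

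The cost is wording in two documents and one derived date, the first open-label dose. No patients or procedures are added. The downside is a shorter post-treatment window for roll-over infants, so a delayed effect of blinded drug would appear only in the separate listing.

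Separately, the sponsor should reconcile these texts; no clinical rule is proposed here:
- **Taper and call timing.** Section 3.1.4 limits the post-Visit 6 taper to infants who do not roll over, but also calls for CBD to be tapered at End of Study. Footnote j says "Similarly, all subjects will be tapered off CBD or CBD Placebo according to the following schedule" and times the call from the end of taper, whereas Section 3.1.5 times it from discontinuation of study drug.
- **Therapies in Follow-up.** The Section 4.7.2 restrictions run through Follow-up, while Section 3.1.3 offers standard-of-care treatment with CBD to infants who may still be in that period.
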